## 5.6 Point of Enrolment

The time at which, following recruitment and before any study-related procedures are undertaken, a participant signs and dates the informed consent form.

## 5.7 Participation duration

It is expected to take approximately 47 weeks to complete participant enrollment. The total duration of the study is expected to be approximately 49-51 weeks from first participant enrolled up to last participant having last visit.

The duration of study participation for an individual subject is expected to be 11 days,  $\pm 3$  days, (from procedure through last visit).

# 6 STUDY INTERVENTIONS

## 6.1 Investigational/Test Device

The BD Spinal NRFit™ Needles (BD Quincke Spinal NRFit™ Needle and BD Whitacre Spinal NRFit™ Needle) are intended to gain entry into or puncture the spinal cavity permitting injection (including anesthesia) / withdrawal of fluids for purposes of diagnostic lumbar puncture and myelography procedures. They consist of a needle, stylet, and needle shield and are available in various gauges and needle lengths. The needle consists of a hollow needle (cannula) bonded to a translucent hub at one end and a specific needle point type (Quincke or Whitacre) at the other end. The stylet has a handle which is color coded and correlates to the gauge size.

The BD Spinal Introducer NRFit™ Needle is intended for placement or introduction of spinal needles. The BD Spinal Introducer NRFit™ Needle consists of a needle, needle hub and needle shield and is available in various gauges. The needle consists of a hollow needle (cannula) bonded to a translucent colored hub (per gauge) at one end and a specific needle point type at the other end. The introducer needle is an optional aid through which a spinal needle can be inserted.

The needle hub of the BD Spinal NRFit™ Needles and the BD Spinal Introducer NRFit™ Needle incorporates ISO 80369-6 compliant connectors. The needle shields are yellow to

indicate that the devices are intended to only connect to ISO 80369-6 (NRFit™) compatible devices such as syringes.

The BD Spinal NRFit™ Needles and the BD Spinal Introducer NRFit™ Needle are sterile, non-toxic and non-pyrogenic. These products are not made with natural rubber latex, Bisphenol A (BPA) or Di-ethylhexyl Phthalate (DEHP).

The BD Spinal NRFit™ Needles and the BD Spinal Introducer NRFit™ Needle are to be used by properly qualified and trained healthcare professionals.

The BD Spinal NRFit™ Needle Sets (BD Quincke Spinal NRFit™ Needle Set and BD Whitacre Spinal NRFit™ Needle Set) consist of either a BD Quincke Spinal NRFit™ Needle or a BD Whitacre Spinal NRFit™ Needle and a BD Spinal Introducer NRFit™ Needle. The indications for use, populations for which the devices are intended, and materials remain the same of those for the BD Spinal NRFit™ Needles and the BD Spinal Introducers NRFit™ Needles.

The BD Syringes NRFit™ (BD Syringe NRFit™ Lok and BD Syringe NRFit™ Slip) are intended for transient use, intended for neuraxial use by healthcare professionals for aspiration/injection of fluids.

They are sterile, single use syringes with ISO 80369-6 (NRFit™) compliant lock or slip connectors. The syringe plunger rod is yellow to designate a device intended to only connect to ISO 80369-6 compatible devices such as spinal needles. These syringes are non-toxic, non-pyrogenic and are not made with natural rubber latex, butylated hydroxytoluene (BHT) or Di-ethylhexyl Phthalate (DEHP).

The BD Spinal NRFit™ Needles, BD Spinal Introducer NRFit™ Needle and BD Syringes NRFit™ are intended for adult and pediatric patients.

Appendix 16.1 provides an overview of the study device variants available for use.

The BD Spinal NRFit™ Needles, BD Spinal Introducer NRFit™ Needle, the BD Spinal NRFit™ Needle Sets, and BD Syringes NRFit™ will be provided by the Sponsor. Devices will either be disposed of at the site according to the site's institutional standard operating procedure or returned to the Sponsor with the appropriate documentation.

Accurate records of all devices received at, dispensed, returned to, and disposed of by the site should be recorded on Study Product Accountability Log.

Aseptic technique and proper preparation are essential for the neuraxial procedure, requiring the physician to wear cap, mask, sterile gloves, and sterile gown. The participant will be covered with a sterile drape and prepped with an appropriate antiseptic agent per procedures guidelines. If a BD Spinal Introducer NRFit™ Needle is used, it is placed between the lumbar vertebrae at the desired interspace and angle. The BD Spinal NRFit™ needle (Quincke or Whitacre) is then inserted through the Introducer NRFit™ needle. The stylet is removed to check for the appearance of CerebroSpinal Fluid (CSF), and then replaced if further advancement of the spinal needle is needed. Once the CSF appears to a satisfactory degree, the medication is delivered through the BD Syringes NRFit™ (Lok or Slip) into the CSF, and the NRFit™ spinal and introducer needles are removed. Site staff may monitor the participant for physiologic and medication effects as part of their routine medical care.

## 6.2 Control Device/Standard of Care

Not applicable. This is a single-arm study.

## 6.3 Ancillary Devices/Products

Neuraxial procedures are conducted under strict aseptic technique and require the physician to wear cap, mask, sterile gloves, and sterile gown. The participant will be covered with a sterile drape and prepped with an appropriate antiseptic agent. Materials used to comply with aseptic technique, including the medication for local skin anesthesia, will be provided by the site according to their site-specific requirements. These products will be used as part of the standard of care of each site. Selected information regarding these products will be collected (See Section 7.3).

Ancillary devices BD Blunt Fill NRFit™ Needles and the BD Blunt Filter NRFit™ Needles are used to aspirate desired medication from an ampule or vial and dose into a BD Syringes NRFit™. They consist of a hollow needle with a blunt needle point, a needle shield and an ISO 80369-6 (NRFit™) compliant, yellow-colored needle hub. The needle hub of the Blunt Filter NRFit™ Needle also has a translucent purple/pink colored portion to indicate that the device contains a filter, while the Blunt Fill NRFit™ Needle has an opaque, red portion. Selected information regarding these devices will be collected (See Section 7.3).

The BD Blunt Fill NRFit™ Needles and the BD Blunt Filter NRFit™ Needles will be provided by the Sponsor. Devices will either be disposed of at the site according to the site's institutional standard operating procedure or returned to the Sponsor with the appropriate documentation.

Accurate records of all devices received at, dispensed, returned to, and disposed of by the site will be recorded on Study Product Accountability Log.

## 6.4 Device Labeling

This study will utilize marketed products. As such, no special labelling is required. However, to ensure that the study devices will be used at the study sites only on behalf of the study, the device packaging will be labeled as "For clinical trial use only" and in the translated format in local languages. Additional details may be found in the Study Supply Plan.

## 6.5 Treatment Allocation and Measures to Minimize Bias

This is a post-market study in which study devices are used as intended. The choice of the specific device is left to the discretion of the clinician.

All the participants will be proposed the study in chronological order when they attend a regular clinic visit, this rule will allow to avoid any selection bias.

All participants potentially fulfilling the inclusion/exclusion criteria will be sequentially offered participation in this study when they attend for a clinical visit prior to performance of neuraxial procedure.

## 7 STUDY PROCEDURES AND ASSESSMENTS

- Study procedures and their timing are summarized in the Schedule of Activities (SoA, Section 1.3).
- Protocol waivers or exemptions are not allowed.
- Adherence to the study design requirements, including those specified in the SoA, is essential and required for study conduct.
- All inclusion/exclusion criteria must be reviewed to confirm that potential participants meet all eligibility criteria. The investigator will maintain a screening log to record details of all participants screened and to confirm eligibility or record reasons for screening failure, as applicable. The investigator will maintain a subject identification log of all the participants enrolled in the study, assigning an identification code linked to their names, alternative subject identification or contact information.
- Procedures conducted as part of the participant's routine clinical management (e.g., blood count) and obtained before signing of the ICF may be utilized for baseline purposes provided the procedures met the protocol-specified criteria and were performed within the time frame defined in the SoA.

### 7.1 Screening and Enrollment

After general screening against inclusion/exclusion criteria, potential participants will be provided with detailed information about the study. For details on the Informed Consent process, please refer to section 14.2. A participant will be considered enrolled once informed consent (or assent as applicable) is signed. Enrolled patients will be assigned a unique participant number.

### 7.2 Medical History / Demography / Baseline Assessments

After enrollment, participant baseline and demographic information will be documented, including, but not limited to:

- Age
- Sex assigned at birth and ethnic origin
- Height and weight (for calculated body mass index)
- Limited Medical history including, but not limited to:
  - Coagulopathy or bleeding disorder
  - History of neurological impairment of the trunk or lower extremities
  - Infection at the site of needle insertion
  - Previous spine surgery at the level involved in the spinal procedure
  - History of chronic or recurring headaches
  - Spine deformity (kyphosis/scoliosis)
- Reason for surgery/intervention (e.g., surgery of lower extremities, surgery of lower abdomen)
- Reason for neuraxial procedure (e.g., analgesia or anesthesia)

- American Society of Anesthesiologists (ASA) physical status (PS) classification. See appendix 16.2 for the definitions and ASA-approved examples [54].

### 7.3 Spinal procedure

Choice of the specific BD Spinal NRFit™ Needle, gauge, length, tip, type and size of a BD Syringes NRFit as well as the option of using a BD Spinal NRFit™ Needle set and BD Spinal Introducer NRFit™ Needle, required for an individual participant is left to the discretion of the clinician. BD Spinal Introducer NRFit™ Needle sizes paired to selected BD Spinal NRFit™ Needles may be used. The devices, participant, aseptic technique, and insertion site will be prepared according to standard medical practices and site-specific procedures.

Ancillary devices are the BD Blunt Fill NRFit™ Needles and the BD Blunt Filter NRFit™ Needles, and they are used to aspirate desired medication from an ampule or vial by connecting the needle hub to a NRFit™ syringe, and to dose into a BD Syringes NRFit™.

If a BD Spinal Introducer NRFit™ Needle is used, it is placed between the lumbar vertebrae at the desired interspace and angle. The BD Spinal NRFit™ needle (Quincke or Whitacre) is then inserted through the Introducer NRFit™ needle. The stylet is removed to check for the appearance of Cerebrospinal Fluid (CSF), and then replaced if further advancement of the spinal needle is needed.

Once the BD Spinal NRFit™ Needle and BD Spinal Introducer NRFit™ Needle, if the latter is used, is successfully placed, the procedure will be completed, injecting the medication through a BD Syringes NRFit™ into the CSF, and removing the NRFit™ spinal and introducer needles.

The devices will be utilized according to the specific medical needs of the participant and site-specific protocols and procedures.

Residents in training program in anesthesia cannot perform the spinal procedure within the study.

#### 7.3.1 Spinal procedure data

Information about the spinal procedure will be documented, including, but not limited to:

- Date and time of NRFit™ Introducer/spinal needle insertion
- Participant position (e.g., lateral position, sitting position)
- Aseptic technique
- Preparation anesthetic medication procedure (e.g., accessories used, including Blunt Fill and Blunt Filter NRFit™ Needles)
- Local anesthetic medication used for local skin anesthesia
- Lumbar Interspace selected for the procedure\*
- Spinal NRFit™ Needle type, gauge, length, catalog number, expire date and lot number

- Spinal NRFit™ Introducer, gauge, length, catalog number, expire date and lot number (if used)
- Syringes NRFit™ type, size, catalog number, expire date and lot number
- Spinal NRFit™ set type, gauge, length, catalog number, expire date and lot number
- Number of spinal needles\*
- Lumbar level at which spinal needle placement was successful
- Medications/agents injected (type, dose, volume)
- Maximum spinal block level measured (left and right) (if performed)
- Adverse events/complications (including but not limited to study endpoints)
- Device deficiencies/failures

\* Physicians performing the spinal procedure may use more than one spinal NRFit™ needle. One reason could be a failure with the device, but frequently it is due to the fact that another spinal NRFit™ needle with a different size may be more suitable for that particular participant, due to an individual participant anatomy for example. In this second case, there is no device failure, just the clinician's preference to use a different needle to achieve procedural success.

Information about the different spinal NRFit™ needles (type, gauge, and length) utilized with the corresponding different interspace levels used during the spinal procedure will be also collected with the reason of failure.

### **7.3.2 Ease of Use Procedure Survey**

After the spinal procedure has been performed and related data is recorded, the clinician performing the procedure will complete a brief survey describing their experience with the procedure to assess the performance of the study / ancillary devices used in the procedure.

## **7.4 Follow-Up**

Participants will be followed through 10-days ( $\pm$  3 days) post procedure to assess for adverse events/complications. Assessments may be performed in a variety of ways, including by telephone, if the participant has been discharged from the hospital prior to day-10 post procedure. The site staff must take advantage of the time window of  $\pm$  3 days only when the 10-day post-procedure occurs during the weekends or holidays. Any adverse event or complication must be diagnosed and confirmed by a study physician. Additional information may also be collected if appropriate.

### **7.4.1 Follow-Up data**

During the required follow-up period the following data will be collected:

- Adverse events/complications

- Post-dural puncture headache (PDPH)

Since there are many causes of headache, it is important that the physicians make the diagnosis of Post Dural-Puncture Headache after sufficient evaluation and being reasonably certain that is the cause of the headache. Post-dural puncture headache is defined as a headache which occurs in the upright/standing position and is relieved when the participant is lying down, provided no other cause of headache could be identified. PDPH is a headache occurring within 5 days of a lumbar puncture, caused by cerebrospinal fluid (CSF) leakage through the dural puncture. It is usually accompanied by neck stiffness and/or subjective hearing symptoms. It remits spontaneously within 2 weeks, or after sealing of the leak with autologous epidural lumbar patch [55]. Participants will be questioned for the presence, severity, onset, duration, and characteristics of headaches, and any other complications. The severity of the headache will be graded from none to mild, moderate, or severe as following [56]:

- None: No PDPH
- Mild: when PDPH caused no interference with daily activities and was treated with no medication or oral analgesics.
- Moderate: when PDPH caused a patient difficulty in performing daily activities and was treated with oral analgesics.
- Severe: a headache that resulted in the patients being unable to perform his or her daily activities or being confined to bed and requiring oral or IV analgesic and/or epidural blood patch for treatment.

## 8 PARTICIPANT DISCONTINUATION/WITHDRAWAL

### 8.1 Discontinuation/Withdrawal

- A participant may withdraw from the study at any time at his/her own request or may be withdrawn at any time at the discretion of the investigator or sponsor for safety, behavioral, compliance, or administrative reasons. This is expected to be uncommon.
- At the time of discontinuing from the study, no further data will be collected for the participant.
- If the participant withdraws consent from the study, he/she will inform the study physician who will record the withdrawal in the source documentation and appropriate section of the electronic case report form.
- If the participant withdraws consent for disclosure of future information, the sponsor may retain and continue to use any data collected before such a withdrawal of consent.
- Participants who withdraw or discontinue the study early (e.g., prior to day-10 post procedure follow-up or prior the procedure) may be replaced.

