## **9 ADVERSE EVENTS AND DEVICE DEFICIENCIES**

### **9.1 Definitions of Events**

#### **9.1.1 Adverse Events (AEs)**

An adverse event is defined as any untoward medical occurrence, unintended disease or injury, or untoward clinical signs (including abnormal laboratory findings) in participants, users, or other persons, whether or not related to the investigational medical devices or procedure and whether anticipated or unanticipated (ISO 14155:2020).

Pre-existing conditions should be considered as part of the participant's medical history and should not be reported as an AE unless there is a substantial increase in severity or frequency of the condition, which has not been attributed to natural history. Likewise, planned hospital visits and/or hospital stays should not be considered as adverse events. Exacerbation of an existing condition should be reported as an AE if the event meets the protocol definition of an AE.

The clinical course of the event will be followed according to accepted standards of medical practice until the event resolves, stabilizes, or in the opinion of the Investigator, is no longer considered clinically significant. The Investigator must supply the Sponsor with information concerning the follow up and/or resolution of the AE.

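### Protocol section 8.1 ends all data collection at any discontinuation, which contradicts the duty in section 9.1.1 to follow adverse events

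*Protocol*

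**What the plan says.** Protocol section 8.1 lets a participant leave at their own request. It also says a participant "may be withdrawn at any time at the discretion of the investigator or sponsor for safety, behavioral, compliance, or administrative reasons". It adds "This is expected to be uncommon" and gives no rate. The next bullet is the data stop: "At the time of discontinuing from the study, no further data will be collected for the participant". It names no reason for discontinuation and makes no exception.

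Withdrawal of consent has its own bullets. Where consent to disclosure of future information is withdrawn, "the sponsor may retain and continue to use any data collected before such a withdrawal of consent". The section ends with replacement: "Participants who withdraw or discontinue the study early (e.g., prior to day-10 post procedure follow-up or prior the procedure) may be replaced".

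Section 9.1.1 says the course of an adverse event (AE) is followed "until the event resolves, stabilizes, or in the opinion of the Investigator, is no longer considered clinically significant". It also obliges the investigator to give the sponsor the follow-up or resolution information. Section 9.4 asks for resolution on the case report form for every AE. Neither section mentions participants who have discontinued.

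On the analysis side, protocol section 10.4 asks that missing data be kept low and uses evaluable data. SAP section 5.2.2 divides PDPH cases by all safety participants, and related AEs by all treated participants. The SAP has no sensitivity analysis for people without a day-10 assessment.

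**The concern.** The study procedure is done once, and everything after it is observation to day 10. Discontinuing a participant after the procedure therefore ends no device exposure; it ends only what is known about that participant. A data stop triggered by any discontinuation creates missing safety data by rule, including when safety was the reason for leaving.

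It also sits oddly beside section 8.2, which asks the site to make every effort to regain contact before declaring a participant lost. A participant who cannot be reached must be chased, while one who can be reached but was withdrawn by the investigator may not be recorded further.

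The affected window matters for the primary safety endpoints. Section 7.4.1 places PDPH onset within 5 days of the puncture, and section 3.1 reports that all literature cases arose within 7 days. A withdrawal in the first days can fall before a headache starts or is diagnosed. No safety committee or data monitoring committee is used, so the site record is the main source of safety evidence.

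**Working it through.** **1. The two rules side by side**

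| Situation | Section 8.1 | Sections 9.1.1 and 9.4 |
|---|---|---|
| AE open when the investigator or sponsor withdraws the participant | No further data | Follow to the defined end point; report follow-up and resolution |
| PDPH or related AE starting after discontinuation, before day 10 | No further data, so not recorded | Would be an AE to record and follow |
| Consent to future disclosure withdrawn | Separate bullet; earlier data may be kept | No exception stated |

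Because consent has its own bullets, the data stop cannot be read as a consent rule only. Nothing in the protocol or SAP reconciles the first row.

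**2. What reaches the primary endpoints**

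Both are incidences (SAP section 5.2.2): PDPH of any severity, and any other AE with a possible, probable or causal relationship. An event recorded before withdrawal is already in the numerator. Its later worsening, seriousness, outcome and duration do not change the incidence, but they do affect the AE summaries in SAP section 7.0, where duration is listed only for AEs with complete dates. The incidences themselves lose only events that start or are diagnosed after discontinuation.

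**3. The plan's own safety figure**

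Section 10.2 gives a 77.9% chance of at least one event at a 1% rate in 150 participants. Check: 1 − 0.99^150 = 0.7785. It reproduces, and the present point does not depend on it.

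**4. Effect of one missed PDPH case**

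Inputs: n = 150 (section 10.2) and the limit of 3% or less (SAP section 1.3), read as a limit on the observed proportion. Since 0.03 × 150 = 4.5, at most 4 cases pass.

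- 4/150 = 2.67% (exact 95% CI 0.73 to 6.69): meets the limit.
- 5/150 = 3.33% (exact 95% CI 1.09 to 7.61): does not.
- Five true cases, one unrecorded after discontinuation: 4/150 = 2.67% if that person is counted as PDPH-free, or 4/149 = 2.68% if dropped. Either passes.

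**5. Direction**

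The direction is not fixed. Suppose four true cases, all recorded, and five event-free participants who left early. Counted as PDPH-free, the result is 4/150 = 2.67%, which is correct. Dropped as not evaluable, it is 4/145 = 2.76%, which is too high.

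**6. Likely scale, by assumption**

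The documents give no withdrawal rate. Assume 1% to 5% of 150 withdraw after the procedure, independently of outcome, with PDPH at the 3% limit. Expected PDPH cases among them run from 150 × 0.01 × 0.03 = 0.045 to 150 × 0.05 × 0.03 = 0.225. Some of these would already be recorded. If withdrawal is linked to symptoms, this range does not apply.

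**The case against.** The strongest reply is that the practical consequence is small. An AE serious enough to prompt withdrawal has normally been seen and recorded first, and section 8.1 does not discard earlier data. Because withdrawal after a single procedure spares no exposure, an investigator has little reason to withdraw a treated participant for safety; such a withdrawal is more plausible before the procedure, when no device outcome is lost. Behavioural, compliance and administrative withdrawals have no stated link to outcome. The change from 4 to 5 cases needs exactly five true cases with one unrecorded, and any single missing case from another cause would do the same. All of this stands as a limit on size. None of it lets a site comply with both rules.

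Three stronger readings are tempting and are not supported.

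- A reader might infer that the rule removes the worst cases. The documents do not show this: the prompting event ordinarily stays in the numerator.
- A reader might infer that both primary safety rates are biased downwards. That follows only if unobserved participants are counted as event-free. The evaluable-data wording in section 10.4 permits another treatment, under which the rate can rise.
- A reader might infer that replacement swaps an unfavourable participant out of the analysis. Protocol section 10.3 and SAP section 4.1 define the treated population by an attempted procedure and the safety population by a successful one (appearance of cerebrospinal fluid), so a later departure removes nobody. The gap is only that section 8.1 does not say so.

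A further fair point concerns the remedy. Someone who asks to leave should not be telephoned merely because they did not expressly refuse data collection; section 14.2 protects the right to withdraw. The fix has to respect that.

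**Conclusion.** The contradiction between section 8.1 and section 9.1.1 is real, and the text should be corrected. The loss has two parts: the later course of events already recorded, and PDPH or related AEs that begin or are diagnosed between discontinuation and day 10.

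Its size cannot be derived from the documents and is probably small if withdrawal is as uncommon as the protocol expects. Understatement of PDPH is conditional on unobserved participants being counted as PDPH-free over all safety participants. Even then, one missed case alters the reading against the 3% limit only when the true count is five. That statement assumes 150 participants in the safety population and a criterion applied to the observed proportion.

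**What to change.** Reconcile sections 8.1 and 9.1.1 as follows.

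- Limit the no-further-data rule to participants who withdraw consent to further data collection.
- For participants withdrawn after the procedure by the investigator or sponsor, and for those who leave but agree to further contact, keep the planned day-10 safety contact and the follow-up of open AEs.
- State in section 8.1 that a treated participant who is replaced stays in the treated population and, where its definition is met, in the safety population.
- In SAP section 5.2.2, say how a participant without a day-10 assessment enters the PDPH and AE denominators, since this decides the direction of any bias.

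The cost is a short revision of the protocol and SAP text and a few additional telephone calls of a type already planned. Sites would also need to record, at discontinuation, whether the participant agrees to further contact.
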